10.4 Publication of study protocol and results

Novartis assures that the key design elements of this protocol will be posted in a publicly accessible database such as clinicaltrials.gov. In addition, upon study completion and finalization of the study report the results of this study will be either submitted for publication and/or posted in a publicly accessible database of clinical study results.

11 Protocol adherence

This protocol defines the study objectives, the study procedures and the data to be collected on study participants. Additional assessments required to ensure safety of patients should be administered as deemed necessary on a case by case basis. Under no circumstances should an Investigator collect additional data or conduct any additional procedures for any research related purpose involving any investigational drugs.

Investigators ascertain they will apply due diligence to avoid protocol deviations. If an Investigator feels a protocol deviation would improve the conduct of the study this must be considered a protocol amendment, and unless such an amendment is agreed upon by Novartis and approved by the IRB/IEC it cannot be implemented. All significant protocol deviations will be recorded and reported in the CSR.

11.1 **Protocol Amendments**

Any change or addition to the protocol can only be made in a written protocol amendment that must be approved by Novartis, Health Authorities where required, and the IRB/IEC. Only amendments that are required for patient safety may be implemented prior to IRB/IEC approval. Notwithstanding the need for approval of formal protocol amendments, the Investigator is expected to take any immediate action required for the safety of any patient included in this study, even if this action represents a deviation from the protocol. In such cases, Novartis should be notified of this action and the IRB/IEC at the study center should be informed within 10 working days or less, if required by local regulations.

12 References

Novartis

	Any event that links to a preferred term (PT) in the MedDRA dictionary falling under the SMQ sub-module "Drug-related hepatic disorders – severe events only"* or any "Hy's law case" PT

^{*} These events cover the following: hepatic failure, fibrosis and cirrhosis, and other liver damage-related conditions; the non-infectious hepatitis; the benign, malignant and unspecified liver neoplasms ALT = alanine aminotransferase, ALP = alkaline phosphatase, AST = aspartate aminotransferase, SMQ = standard medical query, TBL = total bilirubin, UNL= upper normal limit

Table 14-2 Liver event follow-up requirements

Criteria	Event type	Actions required	Follow-up monitoring
Potential Hy's Law case ^a	Medically significant	Discontinue the study drug immediately Hospitalize, if clinically appropriate Report to Novartis as an SAE	ALT, AST, TBL, Alb, PT, ALP and GGT until resolution ^c (frequency at investigator discretion)
ALT or AST		Establish causality	
> 8 x ULN	Medically significant	Repeat LFT within 48 hours If elevation persists, discontinue the study drug immediately Hospitalize if clinically appropriate Report to Novartis as an SAE Establish causality	ALT, AST, TBL, Alb, PT, ALP and GGT until resolution ^c (frequency at investigator discretion)
> 5 to ≤ 8 x ULN	Medically significant	Repeat LFT within 48 hours If elevation persists for more than 2 weeks, discontinue the study drug Report to Novartis as an SAE Establish causality	ALT, AST, TBL, Alb, PT, ALP and GGT until resolution ^c (frequency at investigator discretion)
> 3 x ULN accompanied by symptoms ^b	Medically significant	Discontinue the study drug immediately Hospitalize if clinically appropriate Report to Novartis as an SAE Establish causality	ALT, AST, TBL, Alb, PT, ALP and GGT until resolution ^c (frequency at investigator discretion)
> 3 to ≤ 5 x ULN (patient is asymptomatic)	AESI	Central laboratory to report to Investigator and Novartis Repeat LFT once or twice in the week If elevation persists, establish causality	Investigator discretion Monitor LFT within 1 to 4 weeks or at next visit
≤ 3 x ULN (patient is asymptomatic)	N/A	Repeat LFT at next visit	
ALP (isolated)			
> 5 x ULN	Medically significant	Repeat LFT within 48 hours If elevation persists, report to Novartis as an SAE Establish causality	Investigator discretion Monitor LFT within 1 to 4 weeks or at next visit
> 2 to ≤5 x ULN (patient is asymptomatic)	AESI	Central laboratory to report to Investigator and Novartis Repeat LFT once or twice in the week If elevation persists,	Investigator discretion Monitor LFT within 1 to 4 weeks or at next visit

Criteria	Event type	Actions required	Follow-up monitoring
		establish causality	
≤ 2 x UL N (patient is asymptomatic)	N/A	Repeat LFT at next visit	
TBL (isolated)			
> 3 x ULN	Medically significant	Repeat LFT within 48 hours If elevation persists, discontinue the study drug immediately Hospitalize if clinically appropriate Report to Novartis as an SAE Establish causality	ALT, AST, TBL, Alb, PT, ALP and GGT until resolution ^c (frequency at investigator discretion) Test for hemolysis (eg, reticulocytes, haptoglobin, unconjugated [indirect] bilirubin)
> 1.5 to ≤ 3 x ULN (patient is asymptomatic)	AESI	Central laboratory to report to Novartis Repeat LFT once or twice in the week. If elevation persists, establish causality	investigator discretion Monitor LFT within 1 to 4 weeks or at next visit
≤ 1.5 x ULN (patient is asymptomatic)	N/A	Repeat LFT at next visit	
Preferred terms			
Jaundice	Medically significant	Discontinue the study drug immediately Hospitalize the patient Report to Novartis as an SAE Establish causality	ALT, AST, TBL, Alb, PT, ALP and GGT until resolution ^c (frequency at investigator discretion)
"Drug-related hepatic disorders - severe events only" SMQ AE	Medically significant	Discontinue the study drug hospitalization if clinically appropriate Report to Novartis as an SAE Establish causality	Investigator discretion

^a Elevated ALT/AST > 3 x ULN and TBL > 2 x ULN but with no notable increase in ALP to > 2 x ULN

Alb = albumin, AESI = adverse event of special interest, ALP = alkaline phosphatase, GGT = gamma glutamyl transferase, LFT = liver function test, PT = prothrombin time, SMQ = standard medical query, TBL = total bilirubin, UNL= upper normal limit

^b General malaise, fatigue, abdominal pain, nausea, or vomiting, rash with eosinophilia

^c Resolution is defined as an outcome of one of the following: return to Baseline values, stable values at 3 subsequent monitoring visits at least 2 weeks apart, remain at elevated level after a maximum of 6 months, liver transplantation, and death.

# Document History – Changes compared to previous version of RAP module 3.

#### Version 0.2

- Removal of specific criteria for inclusion in Per-Protocol Set
- Inclusion of new subgroup categories and respective analyses
- Specification of End of Treatment visits
- Modification of EQ-5D analysis: analysis of single dimensions and usage of EQ-5D utility index based on both, GER and UK values
- Analysis of TB status at Baseline
- Inclusion of PK analysis

#### Version 1.0

· No further, contentual changes

#### Version 1.1

- Inclusion of PP-FUS analysis set for the analysis of rebound and relapse
- Removal of indirect response model for PK analysis
- Removal of confidence intervals for risk differences of PASI responder rates
- Inclusion of analysis of AEs of special interest

#### Version 2.0

- Specification of search strategies for AEs of special interest
- Adaption of age groups for baseline description
- Correction of typos

#### List of abbreviations

AE Adverse event

AESI AE of special interest

AIN457 Secukinumab

ALP Alkaline phosphatase

ALT Alanine aminotransferase ANCOVA Analysis of covariance

AST Aspartate aminotransferase

ATC Anatomical therapeutic chemical

BMI Body mass index
BSA Body Surface Area

BSL Baseline

CI Confidence interval
CSR Clinical study report

DLQI Dermatology Life Quality Index

ECG Electrocardiogram

eCRF Electronic case report/record form

EQ-5D EuroQOL 5 Dimension Health Questionnaire

FAS-P75R Full analysis set for Treatment Period 2 of PASI 75 Responders who do

not achieve a PASI 90 Response

FAS-P90R Full analysis set for Treatment Period 2 of PASI 90 Responders

FU Follow-Up
HGB Hemoglobin
HR Heart rate

HRQoL Health-related quality of life

IGA Investigator's global assessment

IGA mod 2011 Novartis investigator's global assessment modified 2011

ITT Intention-to-treat

LLN Lower limit of normal LSM Least-square means

MACE Major adverse cardiovascular events

MCMC Markov Chain Monte Carlo

MedDRA Medical dictionary for regulatory activities

MI Multiple imputation

NMQ Novartis MedDRA Query

NovDTD Novartis Drug and Therapy Dictionary

NRS Numeric rating scale

PASI Psoriasis Area and Severity Index

PD Protocol deviation
PK Pharmacokinetic

PP-P90R Per-Protocol Set for Treatment Period 2 of PASI 90 Responders

PRO Patient Reported Outcome

PT Preferred term

QT interval for heart rate

QTcF QT interval corrected for heart rate using Fridericia's formula

SAE Serious adverse event

SAF-TP1 Safety set for Treatment Period 1 SAF-TP2 Safety set for Treatment Period 2

s.c. Subcutaneous(ly)
SOC System Organ Class

TB Tuberculosis
TBL Total bilirubin

TP1 Treatment Period 1
TP2 Treatment Period 2
ULN Upper limit of normal
VAS Visual analog scale

WPAI-PSO Work Productivity and Activity Impairment Questionnaire-Psoriasis

# 1 Statistical methods planned in the protocol and determination of sample size

Data will be analyzed according to the Section 9 (Data Analysis) of the study protocol (version v01, dated 16 June 2015) which is available in the Appendix of the clinical study report (CSR). Important information is given in the following sections and details are provided, as applicable, in the Appendix of the CSR.

### 1.1 Statistical and analytical plans

This document covers statistical and analytical plans for the analysis of the study CAIN457A3302. This analysis will be performed after all subjects have completed their final visit, i.e. the Week 60 visit for patients entering the Follow-Up period or the Week 52 visit for all other patients, respectively.

The primary objective is to demonstrate in the patient pool of Psoriasis Area and Severity Index (PASI) 90 responders at Week 24 that secukinumab 300 mg subcutaneous (s.c.) every 6 weeks treatment is non-inferior to secukinumab 300 mg s.c. every 4 weeks treatment with respect to maintaining a PASI 90 response rate at Week 52.

The key secondary objective is to demonstrate in the patient pool of PASI 75 responders who do not reach a PASI 90 response at Week 24 that secukinumab 300 mg s.c. administered every 2 weeks is superior to secukinumab 300 mg s.c. administered every 4 weeks at Week 52 based on the PASI 90 response rate.

Other secondary objectives are:

- To evaluate the proportion of PASI 50, PASI 75, PASI 100 and IGA mod 2011 0/1 responder rates at Week 52.
- To evaluate the course of mean PASI over time from Week 24 to Week 52.
- To evaluate the effect of different maintenance treatment frequencies on PROs: Dermatology Life Quality Index (DLQI), EuroQOL 5-Dimension Health Questionnaire (EQ-5D©), Work Productivity and Activity Impairment Questionnaire-Psoriasis (WPAI-PSO), and the patient's assessment of pain, itching and scaling.

#### Exploratory objectives are:

- To evaluate the proportion of PASI 50, PASI 75, PASI 90, PASI 100 and IGA mod 2011 0/1 responders at Week 24.
- To evaluate the time to achieve clear or almost clear skin based on PASI 90 when receiving secukinumab 300 mg s.c. every 2 weeks compared to every 4 weeks from Week 24 to Week 52.
- To evaluate time to first loss of PASI 75 response when receiving secukinumab every 2 weeks compared to every 4 weeks from Week 24 until Week 52.
- To evaluate the safety and tolerability of different maintenance treatment regimens of secukinumab 300 mg s.c.

• To explore the correlation between the pharmacokinetic (PK) data and efficacy outcomes.

Other exploratory objectives for patients with PASI 90 response at Week 24 are as follows:

- To assess the time to loss of PASI 90 response.
- To assess the time to loss of IGA mod 2011 0/1 response.

Summary statistics for continuous variables will include N, mean, standard deviation, minimum, median, maximum. Summary statistics for discrete variables will be presented in contingency tables and will include absolute and relative frequencies.

If not otherwise specified, p-values will be presented as two-sided p-values and two-sided confidence intervals will be displayed. Unless otherwise stated, the level of significance will be set to 5%.

Listings will be presented by treatment sequence, if applicable.

#### 1.1.1 Changes to statistical methods planned in the protocol

- Inclusion of Body Weight at Week 24 as exploratory variable in the key secondary logistic regression model
- No calculation of indirect response models for PK data and efficacy as planned in the protocol. Figures will be provided instead.

#### 1.1.2 Footnotes

Footnotes on outputs will be kept to a minimum also for outputs not covered in Efficacy MAP M7.1 Amendment 5 or Safety MAP M7.1 Amendment 4.

Footnotes will generally be provided for

- abbreviations used in the output; abbreviations used on several outputs, e.g. for listings in the Appendix can be presented on a separate page and do not have to be repeated as footnotes on each listing
- sorting order of categories, e.g. for sorting within MedDRA (Medical Dictionary for Regulatory Activities) hierarchy levels
- MedDRA version used for reporting of MedDRA coded data

Footnotes will generally NOT be given for

- units displayed on the output
- interpretation of results (e.g. "odds ratio larger 1 favors active treatment")
- information that can be retrieved from the statistical section of the Report unless it is not identifiable from the output, e.g.
  - explanation of analysis model used unless results of more than one model are displayed on an output
  - o derivations of variables (e.g. BMI will not be explained in a footnote)
- information that will be provided in the clinical study protocol and/or methods section of the Report (e.g. baseline definition if this is specified in the Report).

### 1.2 Subjects and treatments

The following study periods will be considered for the analysis:

- Screening Period (Screening to Visit 2 [=Baseline], excluding Visit 2 [=Baseline])
- **Treatment Period 1** (Visit 2 [=Baseline] to Week 24 pre-dose)
- Treatment Period 2 (Week 24 post-dose to Week 52)
- Follow-Up Period (Week 52 to Week 60, excluding Week 52).

For Treatment Period 1 (Baseline to Week 24) all patients will receive the same treatment:

• Secukinumab 300 mg s.c. will be self-administered at Baseline, weekly at Week 1, Week 2 and Week 3 and every 4 weeks thereafter (i.e., Week 4, 8, 12, 16 and 20).

At Week 24, all patients will be assessed in term of PASI response and either randomized to one of the 4 treatment groups in Treatment Period 2 (Week 24 to Week 52) or withdrawn from the study. Randomization is stratified by body weight at this visit ("body weight  $\geq 90 \text{ kg}$ " vs. "body weight < 90 kg" at Week 24) in order to ensure balanced allocation of patients to treatment groups within the weight strata.

Patients with at least a 90% reduction in PASI score from Baseline will be randomized at Week 24 on a 1:1 basis to Group 1 or Group 2:

- **Group 1** (recommended maintenance treatment): secukinumab 300 mg s.c. every 4 weeks (Week 24, 28, 32, 36, 40, 44 and 48).
- **Group 2** (experimental dosing maintenance treatment): secukinumab 300 mg s.c. every 6 weeks (Week 24, 30, 36, 42 and 48).

Patients with less than 90% reduction in PASI score from Baseline at Week 24 but who achieved at least a 75% reduction in PASI score from Baseline are eligible for dose frequency intensification and will be randomized on a 1:1 basis to either Group 3 or Group 4:

- **Group 3** (recommended maintenance treatment): secukinumab s.c. 300 mg every 4 weeks (Week 24, 28, 32, 36, 40, 44 and 48).
- **Group 4** (experimental maintenance treatment): secukinumab s.c. 300 mg every 2 weeks (Week 24, 26, 28, 30, 32, 34, 36, 38, 40, 42, 44, 46 and 48).

Patients with a reduction in PASI score from Baseline of less than 75% at Week 24 are not eligible for randomization and are discontinued from the study.

The following analysis sets will be used for the data analysis.

Safety set for Treatment Period 1 (SAF-TP1): The safety set for Treatment Period 1 includes all subjects who took at least one dose of study treatment during this treatment period.

**Safety set for Maintenance Treatment Period 2 (SAF-TP2)**: The SAF-TP2 includes all patients who were randomized and received at least one dose of study drug at or after the Week 24 visit. Subjects will be analyzed according to treatment received.

Full analysis set for Treatment Period 2 of PASI 90 Responders (FAS-P90R): The FAS-P90R will include all patients who were rated as PASI 90 responders at the Week 24 visit, randomized to treatment groups 1 or 2 and received at least one dose of study drug at or after visit Week 24.

Full analysis set for Treatment Period 2 of PASI 75 Responders who do not achieve a PASI 90 Response (FAS-P75R): The FAS-P75R will include all patients who were rated as PASI 75 responders but do not achieve a PASI 90 response at the Week 24 visit, were randomized to treatment groups 3 or 4 and who received at least one dose of study drug at or after visit Week 24.

**Per-Protocol Set for Treatment Period 2 of PASI 90 Responders (PP-P90R): The PP-P90R** will include all patients from the FAS-P90R who complete the study as scheduled without any major deviations from the protocol which may affect the primary outcome of this study. Major deviations will be based on selected protocol deviations as defined in the Data Review Plan and additional criteria which might have impact on the treatment's efficacy. The final classifications of deviations as major (i.e. leading to withdrawal from the PP-P90R) will be performed in a data review before start of the analysis.

**Follow-Up set (FUS):** all patients from dosing group 3 or 4 who entered the Follow-Up (FU) Period of the study, i.e. who continue into the next phase of the trial at Week 52 and for whom any efficacy or safety data from the FU Period are available.

**Per-Protocol Follow-Up set (PP-FUS):** all patients from the FUS without any major deviations from the protocol in the follow-up period which may affect the rebound assessment at the end of this period. The final classifications of deviations as major (i.e. leading to withdrawal from the PP-FUS) will be performed in a data review before start of the analysis.

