9.1 Analysis sets

The **Safety Set for Treatment Period 1 (SAF-TP1)** will include all patients who received at least one dose of study drug during this treatment period.

The Safety Set for Maintenance Treatment Period 2 (SAF-TP2) will include all patients who were randomized and received at least one dose of study drug at- or after the Week 24 visit. For safety evaluations, the patient groups of PASI 90 responders and PASI 75 responders who do not achieve a PASI 90 response will be pooled; therefore, only 3 dosing groups will be compared:

- secukinumab 300 mg s.c. every 2 weeks (patients from Group 4)
- secukinumab 300 mg s.c. every 4 weeks (patients from Group 1 pooled with Group 3)
- secukinumab 300 mg s.c. every 6 weeks (patients from Group 2)

Patients will be analyzed according to the treatment they received.

The Full Analysis Set for Treatment Period 2 of PASI 90 Responders (FAS-P90R) will include all patients who are rated as PASI 90 responders at the Week 24 visit, were randomized to treatment groups 1 or 2 and who received at least one dose of study drug at- or after visit Week 24.

The Full Analysis Set for Treatment Period 2 of PASI 75 Responders who do not achieve a PASI 90 Response (FAS-P75P) will include all patients who are rated as PASI 75 responders who do not achieve a PASI 90 response at visit Week 24, were randomized to treatment Group 3 or 4 and who received at least one dose of study drug at- or after visit Week 24.

The Per-Protocol Set for Treatment Period 2 of PASI 90 Responders (PP-P90R) will include all patients from the FAS-P90R who complete the study as scheduled without any major deviations from the protocol which may affect the primary outcome of this study. Such deviation will be defined in the Data Validation Plan or similar document and in the protocol of the blind data review without knowledge of the treatment group assignment.

Efficacy evaluations will be performed according to the treatment assigned at randomization.

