#### 1.8.2 Statistical hypothesis, model, and method of analysis

The statistical null-hypothesis to be rejected in the primary analysis is that the odds ratio of maintaining a PASI 90 response for patients with secukinumab 4-weekly dosing versus patients on secukinumab 6-weekly dosing exceeds the non-inferiority margin of  $1+\delta$ .

The primary hypothesis is stated as follows:

Let  $\pi_j$  denote the probability of a PASI 90 response at Week 52 for dosing group j, j=0, 1, where

- 0 corresponds to 4-weekly dosing
- 1 corresponds to 6-weekly dosing

The following hypothesis will be tested

$$H_{01}$$
:  $(\pi_0 / (1 - \pi_0)) / (\pi_1 / (1 - \pi_1)) \ge 1 + \delta$  versus  $H_{A1}$ :  $(\pi_0 / (1 - \pi_0)) / (\pi_1 / (1 - \pi_1)) < 1 + \delta$ 

The non-inferiority margin  $1+\delta$  is calculated as 2.23 assuming a PASI 90 response maintenance rate of 81.8% under 4-weekly dosing treatment scheme and using a 15% non-inferiority margin. The **primary analyses** will be performed comparing dosing groups (Group 1 vs. Group 2) with respect to the primary efficacy variable in a logistic regression model with the factors dosing group, country, PASI 90 response at Week 16 (Yes, No) and body weight at Week 24 (< 90 kg or  $\geq$  90 kg, for model definition see Section 2.2.2). The odds ratios and their two-sided 95%-Wald confidence intervals (CIs) will be given.

In case of subgroup analyses where the grouping variable is one of the above described factors in the logistic regression model the respective factor is excluded from the model.

Additionally, the one-sided p-value for the shifted null-hypothesis will be given. The respective test statistic is calculated as

$$\frac{\hat{\beta}-\beta_0}{se_{\hat{\beta}}}$$

where  $\hat{\beta}$  is the type 3 maximum likelihood estimate of the dosing group parameter in the logistic regression model and  $se_{\hat{\beta}}$  is its standard error.  $\beta_0$  is the non-inferiority margin of the estimator which corresponds to the  $\delta$  from the above null-hypothesis and is therefore set to  $ln(1+\delta) = ln(2.23) = 0.80$ .

Only in case that the number of patients with response (or non-response) in one of the groups is 5 or lower, exact logistic regression will be used for the primary analysis instead of logistic regression using maximum-likelihood based estimators.

The primary analysis set will be the FAS-P90R.

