#### 1.8.3 Handling of missing values/discontinuations

Patients who drop out prematurely and/or do not have a valid PASI assessment at Week 52 will be counted as non-responders. Patients with major protocol violations, but with a valid PASI assessment will be included in the intention-to-treat (ITT)-analysis (i.e. primary analysis) with their observed response. The same algorithm will be used for the key secondary endpoint, the PASI 90 response at Week 52 in the FAS-P75R set. Missing values for secondary endpoints or other outcomes (e.g. quality of life, safety or lab measurements) will not be replaced.

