#### 1.8.4 Supportive analyses

Sensitivity analyses for the primary outcome will be performed as follows:

- (A) In addition to the logistic regression model the risk difference for PASI 90 response at Week 52 between Group 1 and Group 2 will be computed with the corresponding 95%-CI (asymptotic Wald CIs with continuity correction) using the SAS PROC FREQ procedure with the RISKDIFFC option.
- (B) The primary analysis (logistic regression analysis) and the analysis of risk difference will be repeated for the PP-P90R set.
- (C) An analysis based on multiple imputations of the PASI 90 response at Week 52 will be performed. Details are described in Section 2.2.3.

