#### 2.2.3 Multiple imputations for response variables

Non-responder imputation as primary analysis will be performed since low drop-out rates are expected. It is expected that subjects will be likely to drop-out due to lack of efficacy, such that a non-responder imputation will be reasonable.

In the multiple imputations analysis the response status will be imputed based on the individual treatment arm information.

Multiple imputation (MI) is a simulation based approach where missing values are replaced by multiple Bayesian draws from the conditional distribution of missing data given the observed data and covariates, creating multiple completed data sets. These completed data sets can then be analyzed using standard methods. Rubin (1987) presented rules how to combine the multiple sets of estimates to produce overall estimates and confidence intervals that adequately incorporate missing data uncertainty.

Missing values for the 'change from baseline PASI score' will be imputed based on an underlying joint normal distribution and using a Markov Chain Monte Carlo (MCMC) method. The change from baseline in PASI score appears to follow closer to a normal distribution than the actual PASI score.

Page 41

The imputations will be done separately for each dosing group including weight at Week 24 (in groups) as additional covariate. Values post assessment timepoint of the primary endpoint will not be considered for imputations.

The number of imputations will be set to 50, the seed for the random function will be set to 4573302 for this study. To generate the multiple imputed data sets, the SAS procedure MI can be used as follows:

The input data set <pasi> should have one record per subject with baseline PASI score as well as all changes from baseline PASI starting with Week 28.

```
ODS LISTING CLOSE;
ODS OUTPUT MissPattern=miinfo_msgpat VarianceInfo=varinfo ParameterEstimates=param;
PROC MI DATA=<pasi> OUT=<impdata> SEED=4573302 NIMPUTE=50;
 VAR <weight at Week 24> >
     <baseline PASI>
     <change from baseline PASI week 24> - <change from baseline PASI week primary endpoint>;
RUN;
ODS LISTING;
```

Two outputs will be prepared displaying i) the missing data patterns and the group means as stored in the data set msgpat and ii) the variance information and estimated means with confidence interval and range based on data sets varinfo and param which need to be merged by <dosing group>.

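### The per-protocol set PP-P90R admits only completers, so early stops for lack of efficacy drop out of the supportive non-inferiority analyses, which can bias them in either direction

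*SAP*

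**What the plan says.** - **Entry to the set.** SAP 1.2 defines PP-P90R as the set that "will include all patients from the FAS-P90R who complete the study as scheduled without any major deviations from the protocol". Protocol 9.1 likewise requires that patients "complete the study as scheduled without any major deviations from the protocol which may affect the primary outcome of this study". Neither makes an exception for stopping because the treatment no longer works.
- **Use of the set.** SAP 1.8.4: "The primary analysis (logistic regression analysis) and the analysis of risk difference will be repeated for the PP-P90R set".
- **Primary analysis.** SAP 1.8.2: "The primary analysis set will be the FAS-P90R". SAP 1.8.3: "Patients who drop out prematurely and/or do not have a valid PASI assessment at Week 52 will be counted as non-responders".
- **Expected reason for leaving.** SAP 2.2.3: "It is expected that subjects will be likely to drop-out due to lack of efficacy". The same section expects drop-out to be low. No rate by arm is given anywhere.
- **Status after stopping drug.** Under protocol 5.5.10 the patient has an early end-of-treatment visit and is registered in the IRT as having completed early. The section also says that such patients are not regarded as discontinued from the study.
- **Who classifies deviations.** Protocol 9.1 refers to a "blind data review without knowledge of the treatment group assignment". SAP 1.2 says only that the final classification "will be performed in a data review before start of the analysis".

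**The concern.** A per-protocol set is meant to remove patients whose conduct departed from the protocol. A patient who took every dose, lost response on the assigned interval and then stopped has not departed from it; that patient is a treatment failure. The completion condition removes the failure along with the deviators, so membership of PP-P90R depends partly on the outcome being compared.

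This matters because the per-protocol repeat is normally read as corroboration of a non-inferiority result. If the failures removed are unevenly spread between arms, agreement or disagreement between the two sets may reflect who was removed rather than the effect of the dosing interval. Uneven stopping is plausible here, since the sample size section allows 6-weekly dosing to be up to 7 points worse.

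**Working it through.** **1. Reproduce the plan's figures.** Inputs from SAP 1.11 and 1.8.2: 81.8% vs 74.8%, margin 15 points, one-sided 2.5%, 90% power, 570 randomised per group, odds-ratio limit 2.23.

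- n = (1.960 + 1.282)² × (0.818×0.182 + 0.748×0.252) / (0.15 − 0.07)² = 553.9, so 554 per group, as stated.
- Limit = (0.818/0.182) / (0.668/0.332) = 2.234, matching 2.23.

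**2. What removal does.** In each arm let p be the FAS response rate and d the share of randomised patients who stop early for lack of efficacy. They are FAS non-responders and are missing from PP-P90R. Subscript 0 is 4-weekly and 1 is 6-weekly.

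- PP rate = p/(1 − d); PP odds = p/(1 − p − d).
- With f = d/(1 − p), the fraction of non-responders who stop, PP odds ratio = FAS odds ratio × (1 − f1)/(1 − f0). It falls, favouring 6-weekly, only if f1 > f0.
- The PP risk difference falls if p1·d1/(1 − d1) > p0·d0/(1 − d0). For small d this is d1/d0 > p0/p1 = 0.818/0.668 = 1.22.

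At the margin, with 5% stopping on 4-weekly, the odds-ratio break-even on 6-weekly is 5 × 33.2/18.2 = 9.1%.

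**3. Example, 3%/8% at the margin.** PP rates are 0.818/0.97 = 84.3% and 0.668/0.92 = 72.6%, a difference of 11.7 points. PP odds are 0.818/0.152 = 5.38 and 0.668/0.252 = 2.65, an odds ratio of 2.03.

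**4. Chance of meeting the limit when the truth is at the margin (81.8% vs 66.8%).** Simulation with 570 per arm, 400,000 runs and no covariates. The odds ratio uses the Wald interval against 2.23. The risk difference uses the continuity-corrected Wald interval against 15 points. Stop rates are assumptions.

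| Stops, 4-weekly/6-weekly | PP difference (points) | PP odds ratio | Meets 2.23 | Meets 15 points |
|---|---|---|---|---|
| none removed | 15.0 | 2.23 | 2.5% | 2.1% |
| 2%/4% | 13.9 | 2.21 | 3.0% | 5.7% |
| 3%/6% | 13.3 | 2.19 | 3.3% | 9.0% |
| 3%/8% | 11.7 | 2.03 | 9% | 24% |
| 5%/10% | 11.9 | 2.15 | 4.2% | 23% |
| 5%/15% | 7.5 | 1.69 | 39% | 86% |
| 4.6%/8.3% (25% of non-responders in each arm) | 12.9 | 2.23 | 2.5% | 12% |
| 5%/5% | 15.8 | 2.62 | 0.1% | 0.9% |
| 6%/3% | 18.2 | 3.03 | <0.1% | <0.1% |

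At the planning rates (81.8% vs 74.8%) with 5%/10%, the difference shrinks from 7.0 to 3.0 points and the odds ratio from 1.51 to 1.26.

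**5. After the fix.** If these stops stay in as non-responders and other exclusions are ignored, the first row applies again: about 2.5% and 2.1%.

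**The case against.** **No confirmatory claim rests on this set.** That stands. SAP 1.8.6 ties the claim to the odds ratio from the primary model, and that model is fitted in FAS-P90R with drop-outs as non-responders. Multiple imputation and a FAS risk difference are further supportive analyses. Time to loss of PASI 90 response is analysed in FAS-P90R, and SAP Table 2-1 lists lack-of-efficacy discontinuation under informative censoring. SAP 1.5.1 reports discontinuation reasons by set.

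**The effect is small if drop-out is low.** This also stands. At 2%/4% the odds-ratio figure barely moves (3.0% against 2.5%). The 39% and 86% in the table need 5% against 15%, which the documents neither predict nor exclude.

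**Protocol 5.5.10 keeps patients in the study after they stop drug.** This does not remove the problem. They have an early end-of-treatment visit and are registered as early completions, which is hard to read as completing on schedule.

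Three stronger readings are tempting but not supported:

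- A reader might infer that the per-protocol analysis is necessarily tilted towards 6-weekly, with no bias when stopping is equal. More stops on 6-weekly are not enough on the odds-ratio scale: at 5%/8% the PP odds ratio is 2.34, worse for 6-weekly than the FAS value. Equal absolute rates of 5%/5% raise it to 2.62.
- A reader might infer that every patient who loses response leaves. Loss of PASI 90 is not among the mandatory reasons for stopping in protocol 5.5.10. Such a patient may stay to Week 52 and count as a PP non-responder. Only early stops are lost.
- A reader might infer that the SAP has abandoned the blind review. SAP section 1 applies protocol Section 9, which contains it, and SAP 1.1.1 declares no change. SAP 1.2 is silent on blinding; it does not contradict the protocol.

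**Conclusion.** The concern holds in conditional form. The completion requirement excludes patients on an outcome-related event that the SAP itself expects, so PP-P90R is a weak check on the primary result. The documents do not settle the direction or size of the bias, because both depend on stop rates by arm that they do not give.

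The risk difference is the more exposed measure. At the margin it favours 6-weekly once the ratio of stops exceeds about 1.2, even when the same fraction of failures leaves each arm. It is also the scale on which protocol 9.4.3 defines the margin. The odds ratio is more robust and can move against 6-weekly.

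The figures assume 570 per arm, unadjusted analyses, no other per-protocol exclusions, and that every removed stop is a FAS non-responder. The confirmatory FAS conclusion is unchanged in every scenario. The point deserves correction because the per-protocol results are likely to be read as corroboration, not because the trial's claim is at risk.

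**What to change.** 1. In SAP 1.2, keep in PP-P90R, as non-responders, patients who stopped for lack of efficacy and had no major deviation up to that point. Alternatively, leave PP-P90R as defined and report this analysis beside it, for both the odds ratio and the risk difference.
2. Declare the change in SAP 1.1.1, since protocol 9.1 carries the completion condition. Rewriting protocol 9.1 itself would need an amendment under protocol 11.1; the added analysis avoids that.
3. As a clarification, state in SAP 1.2 that deviations are classified without knowledge of treatment group, as protocol 9.1 already requires.

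Cost: SAP wording and one more output. The primary reason for stopping study drug is already recorded under protocol 5.5.10, so no new data are needed. Per-protocol response rates will be slightly lower.
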